11.4 ELECTROCARDIOGRAM (ECG)

Descriptive statistics are provided for ECG parameters (e.g., Heart Rate, PR interval, QRS interval, QT interval, and QTc interval) at baseline and changes from baseline at each assessment time point. QTc interval is calculated using both Bazett ($QTcB = QT/(RR)^{1/2}$) and Fridericia ($QTcF = QT/(RR)^{1/3}$) corrections; and if RR is not available, it is replaced with 60/HR in the correction formula.

13 APPENDIX 1: DATA HANDLING CONVENTIONS**13.1 VISIT TIME WINDOWS**

| Endpoint | Visits during Treatment Period | | | | |
|---|--------------------------------|-----------------------------|----------------------|---|------------------------------------|
| | Every 4 weeks ^a | Every 24 weeks ^b | Target Day | Analysis Visit Windows Actual Assessment Day ⁺ | Analysis Visit ⁺⁺ |
| | | | Day 1 | Day 1 | Baseline |
| BP, HR, respiratory rate* | X | | Day 7 * (Week #) + 1 | Target Day plus or minus half the duration to the next Target Day | Weeks 4, 8, 12 then every 12 weeks |
| 12-lead ECG | | X | Day 7 * (Week #) + 1 | [Target Day – 84, Target Day + 83] | Week 24, 48, ... |
| Hb, reticulocyte count, CHr* | X | | Day 7 * (Week #) + 1 | Target Day plus or minus half the duration to the next Target Day | Weeks 4, 8, 12 then every 12 weeks |
| CBC with WBC differential * | X | | Day 7 * (Week #) + 1 | Target Day plus or minus half the duration to the next Target Day | Weeks 4, 8, 12 then every 12 weeks |
| Fasting serum chemistry (including LFTs, lipid panel, glucose) | X | | Day 7 * (Week #) + 1 | Target Day plus or minus half the duration to the next Target Day | Weeks 4, 8, 12 then every 12 weeks |
| Serum iron, ferritin, transferrin (or TIBC), TSAT | X | | Day 7 * (Week #) + 1 | Target Day plus or minus half the duration to the next Target Day | Weeks 4, 8, 12 then every 12 weeks |
| Special labs (CHr, hepcidin, hs-CRP, plus exploratory biomarkers) ^l | | X | Day 7 * (Week #) + 1 | [Target Day – 42, Target Day + 41] | Week 24, 48, ... |
| 
Abbreviations: BP = blood pressure; CBC = complete blood count; CHr = reticulocyte hemoglobin content; CRP = C-reactive protein; ECG = electrocardiogram; HR = heart rate; LFT = liver function test; TIBC = total iron binding capacity; TSAT = transferrin saturation; WBC = white blood cell.
 
* Visit weeks are weekly (week 1 to 4), every 2 weeks (week 6 to 24), every 4 weeks afterwards
 
a Visit weeks may include of: Weeks 13, 37, 61, 85, 109, 133, 157, 181, 205, 229, and 253
 
b Visit weeks may include of: Weeks 25, 49, 73, 97, 121, 145, 169, 193, 217 and 241
 
++ Analysis visits are up to the EOT, which is the last day of treatment.
 
Note: The lower bound for the first visit window starts at Day 1.
 | | | | | |

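### The SAP 13.1 window rule uses the forward gap on both sides, so windows overlap wherever visit spacing widens; on the Analysis Visit weeks, Week 8 lies wholly inside Week 12

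*SAP*

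**What the plan says.** The table in SAP 13.1 sets each target day at 7 × week number + 1. For the Hb, CBC, vital-sign, chemistry and iron rows the window is "Target Day plus or minus half the duration to the next Target Day". A note opens the first window at Day 1.

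The table does not say which weeks are the targets. It offers several lists:
- the Analysis Visit column: "Weeks 4, 8, 12 then every 12 weeks";
- the column heading for 4-weekly assessments;
- footnote *, attached to the Hb, CBC and vital-sign rows: "Visit weeks are weekly (week 1 to 4), every 2 weeks (week 6 to 24), every 4 weeks afterwards";
- footnote a: "Visit weeks may include of: Weeks 13, 37, 61, 85, 109, 133, 157, 181, 205, 229, and 253".

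Other sections decide which value represents a visit. SAP 5.3 uses derived analysis visits for all outputs. Where a scheduled visit has several measurements it takes the last, or the maximum for CPK, WBC and liver tests. SAP 13.2, on repeated or unscheduled safety assessments, takes the last one in the window. SAP 10.1 summarises the efficacy endpoints at the 13.1 visits and describes the Hb ≥10 g/dL endpoint as a mean over selected periods.

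**The concern.** A window of plus or minus half the gap to the next target is sound only when targets are evenly spaced. When spacing widens, the longer forward gap is also applied backward and the window reaches into the previous one. All the candidate lists that start with close visits and then spread out have this feature.

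At stake are the by-visit tables of Hb (the primary objective), blood pressure, lipids, chemistry and iron. Two programmers following 13.1 could put the same result under different weeks, or under two weeks at once. On the Analysis Visit targets, windows of up to 84 days also hold several scheduled visits, so the rule for choosing a value decides how far the reported result lies from its label.

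**Working it through.** **Inputs.** Target day T = 7 × week + 1 and half-width h = (next T − T)/2, both from SAP 13.1. The first window opens at Day 1.

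**Which list fits the table's own figures.** The ECG row prints −84/+83 days around Weeks 24 and 48. Those targets are 168 days apart and half of that is 84, so the ECG row fits the Analysis Visit column as the target list, with half-open ends. The special-labs row ("Target Day – 42, Target Day + 41" around the same weeks) does not fit it.

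**Analysis Visit targets.**

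| Week | T | h | Literal window | Midpoint window |
|---|---|---|---|---|
| 4 | 29 | 14 | 1-43 | 1-43 |
| 8 | 57 | 14 | 43-71 | 43-71 |
| 12 | 85 | 42 | 43-127 | 71-127 |
| 24 | 169 | 42 | 127-211 | 127-211 |

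Week 8 is contained in Week 12, an overlap of 71 − 43 = 28 days. With half-open ends it is 43-70 inside 43-126, so the nesting remains. It is the only overlapping pair on this list apart from shared end days.

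**Footnote * targets.** Week 3 = 22 ± 3.5 = 18.5-25.5 and Week 4 = 29 ± 7 = 22-36, an overlap of 3.5 days. Week 22 = 155 ± 7 = 148-162 and Week 24 = 169 ± 14 = 155-183, an overlap of 7 days.

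**Evenly spaced 4-weekly targets.** Week 8 = 43-71, Week 12 = 71-99, Week 24 = 155-183. Only end days are shared.

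**Double use on Analysis Visit targets.** With 4-weekly visits the Week 12 window holds Weeks 8, 12 and 16. If a liver-test, CPK or WBC peak at Week 8 (Day 57) is the highest of the three, it is the maximum for both Week 8 and Week 12. In a mean, 1 of the 3 readings is shared. On the Appendix A schedule with half-open ends, Week 12 holds Weeks 6 to 16 (six readings), of which 2 (Weeks 6 and 8) are also in Week 8.

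**Lag if the last value in the window is taken.** There are 28 analysis visits to Week 312: Weeks 4, 8, 12, and (312 − 24)/12 + 1 = 25 more. Weeks 12-300 are 25 of them. Bounds are half-open.
- *On the 4-week grid.* Week 24 = Days 127-210 holds Weeks 20, 24 and 28 (Days 141, 169, 197). The last is 4 weeks late. The same holds at all 25 visits.
- *Off the grid.* SAP 3 and Protocol 4.1 give 2-weekly visits for the first 104 weeks, counting time in the earlier study, then 4-weekly. Protocol 1.6.2 gives 16-24 weeks in Study 041, so the switch falls at Weeks 80-88 here. Six weeks in Study 040 puts it at Week 98. After a switch at Week 98, visits fall at Weeks 102, 106, 110 and so on. Week 108 (T = 757) = Days 715-798 holds Weeks 102, 106 and 110, so the last is 2 weeks late.

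| Switch | 4 weeks late | 2 weeks late |
|---|---|---|
| On the grid (e.g. Week 80 or 88) | 25 | 0 |
| Week 82 or 86 | 6 (Weeks 12-72) | 19 |
| Week 98 | 7 (Weeks 12-84) | 18 |

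Closed bounds, the literal reading, can lengthen this: with 2-weekly visits, Week 12 closes on Day 127 = Week 18, which is 6 weeks late.

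**Does the repair work?** Midpoint windows remove every overlap beyond a shared end day, and half-open ends remove that. They do not cure the lag alone: with 4-weekly visits, Week 12 (Days 71-126) still ends on Week 16. Taking the closest value gives zero lag at all 28 visits on the 4-week grid. Off it, lag is zero at only 8-10 visits, and 17-19 visits have two values each 2 weeks from target. A tie rule is therefore needed.

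**The case against.** The strongest defence is that next target was meant as the adjacent target on each side. SAP 5.3 points that way when it groups unscheduled visits with the closest scheduled one. But that sentence covers unscheduled visits only and does not alter the window printed in 13.1.

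It can also be said that the nesting depends on one target list. That is partly right: with evenly spaced 4-weekly targets there is no overlap, and on footnote * the overlapping pairs each include a week (3 or 22) that is not in the Analysis Visit column, so tabulated visits would share at most an end day. What stands is that the list is not named, that the ECG row fits the one that nests, and that the formula fails on both lists with changing spacing.

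Three stronger readings are tempting and are not supported:
- *Results are 4 weeks late on any visit calendar.* This holds only when visits fall on the 4-week grid. It also presumes that the last-value rules reach across several scheduled visits in one window. SAP 5.3 speaks of several measurements at one visit and 13.2 of repeated or unscheduled safety tests, so for that case no rule may be stated at all.
- *Hb has two competing summary rules.* SAP 10.1 is the specific Hb rule, averaging over a period. The 5.3 rule can resolve duplicates at one visit before averaging. Both can apply; what is missing is a sentence saying so.
- *Conclusions are affected.* The analysis is descriptive and uncontrolled, with no test or comparison.

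Two side points are marginal. CHr appears in both "Hb, reticulocyte count, CHr" and "Special labs (CHr, hepcidin, hs-CRP, plus exploratory biomarkers", but the protocol schedules it only at baseline, every 24 weeks and at termination. Footnotes a and b differ by a week from the Analysis Visit numbering and only list weeks that may be included.

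Finally, the window column carries a + mark whose note is absent from this copy, and SAP 1 places table specifications in a separate document. Either may settle part of this.

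**Conclusion.** Wrong as written. The formula in 13.1 produces overlapping windows wherever visit spacing widens: 28 days and full nesting for Weeks 8/12 on the Analysis Visit targets, and 3.5 and 7 days on the footnote * targets. That is a faulty rule and not merely a missing detail, although the missing target list makes it worse. The overlap figures follow from the SAP alone.

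The lag of 2 to 4 weeks for Weeks 12-300 rests on four assumptions: Analysis Visit targets, half-open bounds, the last value in the window, and visits attended on schedule to Week 312.

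The consequence is limited to when by-visit results are shown to occur, and whether they can be reproduced, in 15 subjects. Listings keep every assessment, and all post-baseline assessments count toward potentially clinically significant values (SAP 13.2).

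**What to change.** In SAP 13.1:
- Name the Analysis Visit column as the target list for these rows.
- Replace the formula with printed, non-overlapping windows bounded at the midpoint to each adjacent target: Baseline = pre-dose; Week 4 = Days 2-42; Week 8 = Days 43-70; Week 12 = Days 71-126; Week 24 = Days 127-210; Week 36 = Days 211-294; and so on to end of treatment.
- For single-value summaries, use the value closest to the target day, with a stated tie rule (for example, the later value).
- Say that the maximum for CPK, WBC and liver tests is then taken over the printed window. This extends the 5.3 rule, which speaks of one scheduled visit, so it should be explicit.
- State that the Hb endpoints in 10.1 average the central-laboratory values in the printed window, and that the last-value rule in 5.3 only resolves several measurements at one visit.
- Reconcile these periods with the dose periods in SAP 8.1 (every 4 weeks to Week 24, every 8 weeks for Weeks 25-48, then every 12), since 10.1 plots Hb and dose together.
- If the + note or the table specifications already fix any of this, cite them in 13.1.

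The cost is SAP wording and minor programming. No new data are needed.

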7.1.1. Treatment Period

7.1.1.1. Baseline (Week 1)

The following assessments will be performed prior to study drug administration. Assessments performed at the end-of-study visit in the previous roxadustat study may be used for those assessments noted below that need to be completed within 4 weeks prior to study drug administration.

- Signed written informed consent within 4 weeks prior to study drug administration;
- Inclusion criteria verification;
- Exclusion criteria verification;
- Vital signs: BP, heart rate (HR) and respiratory rate;
- Complete physical examination within 4 weeks prior to study drug administration;
- Weight (use dry weight in HD subjects) within 4 weeks prior to study drug administration;
- 12-lead ECG within 4 weeks prior to study drug administration;
- Quality of Life questionnaire (FACT-An) within 4 weeks prior to study drug administration.
- Laboratory tests:
 - CBC with white blood cell (WBC) differential and reticulocyte count;
 - Fasting serum chemistry (with LFTs, lipid profile, and glucose);
 - Human chorionic gonadotropin (hCG) test within 4 weeks prior to study drug administration (for women of childbearing potential only);
 - Serum iron studies: iron, ferritin, transferrin (or total iron binding capacity [TIBC]), and TSAT;
 - Special laboratory tests (CHr, hepcidin, hs-CRP, plus select biomarkers) within 4 weeks prior to study drug administration (only for subjects who had a baseline collected during prior roxadustat study);
- Adverse events;

- Concomitant medications;
- Dispense roxadustat (2-week supply for subject previously assigned to roxadustat and 1 week supply for newly initiated to roxadustat with unstable Hb).

7.1.1.1.1. Weekly Visits (± 3 days) up to week 4

- Weekly visits are only for the optional group of subjects newly initiated to roxadustat and only need to be performed until Hb stabilizes.
- Dispense weekly roxadustat
- Vital signs: BP, HR, and respiratory rate
- Laboratory tests:
 - CBC with WBC differential and reticulocyte count
- Adverse events
- Concomitant medications

7.1.1.1.2. Every 2 Week Visits (± 3 days) up to week 24

- Dose Adjustments as needed
- Dispense roxadustat
- Vital signs: BP, HR, and respiratory rate
- Laboratory tests:
 - CBC with WBC differential and reticulocyte count
- Adverse events
- Concomitant medications

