5.3 ADDITIONAL DATA HANDLING RULES AND PRESENTATION SPECIFICATIONS

The following general guidelines apply to all statistical analyses and data presentations:

- The baseline Hb value for efficacy analysis is defined as the mean of the central laboratory Hb value from the baseline visit at Day 1 (prior to receiving the first dose of study drug in this study), plus any other central lab Hb values within 15 days prior to Day 1
- Baseline of other assessments is defined as the last available value obtained prior to the first dose of study drug in this study, unless otherwise specified in this SAP.
- Analysis visits (instead of the nominal visits from CRF) derived from visit dates and visit time windows are used in all analyses, tables, listings and figures. Unscheduled visits within an allowable window are grouped into the closest scheduled visits based on the visit window specified in Appendix 1. For subjects who have more than one measurement at a scheduled visit, the last measurement issued, with the exception of CPK, WBC, liver function tests (i.e., ALT, AST, GGT, ALP, and total bilirubin), in which the maximum measurement issued.
- By default, US conventional units are used for laboratory value presentations. A set of lab summary tables in SI units are also provided based on TLF index.
- Age is calculated as of date that the informed consent form was signed.
 - age = INTCK('YEAR', Birth Date, Date of Informed Consent, 'C')where INTCK is a SAS function.
- Body weight, height and temperatures are converted using the following formula:
 - kg = lb/2.2
 - cm = 2.54 x in
 - C° = (5/9) x (F° – 32)
- For continuous variables that are recorded as “<X” or “>X”, the value of “X” issued in the calculation of summary statistics.
- The mean, standard deviation and median is presented with adding one more decimal to raw data with rounding off. The minimum and maximum is presented with the same number of decimals as in the raw data.
- All percentages are rounded to one decimal place and lined up by the decimal place. The percentage is suppressed when the count is zero.
- Any p-values are rounded to four decimal places and presented as ‘<.0001’ if they are less than 0.0001 before rounding.
- All tables and listings have a header showing “FibroGen, Inc.”, the protocol number, date of the database transfer, and Page x of y. A footer shows the program file path/name, output file path/name, run date and run time.

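### SAP 13.1 puts Day 1 in both Baseline and the first visit window, so a pre-dose value can enter the first post-baseline Hb, maximum-rule laboratory and special-lab summaries; the effect is minor and one sentence fixes it.

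*SAP*

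**What the plan says.** The first row of the table in SAP 13.1 reads "Day 1 | Day 1 | Baseline". The next rows define post-baseline windows. For vital signs, Hb, CBC, chemistry and iron the window is "Target Day plus or minus half the duration to the next Target Day", with Week 4 as the first analysis visit. For ECG it is "Target Day – 84, Target Day + 83", with Week 24 first; special labs use a narrower window around the same target. The note below the table says: "Note: The lower bound for the first visit window starts at Day 1".

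Baseline is a pre-dose quantity throughout. SAP 5.3 builds baseline Hb from the "baseline visit at Day 1 (prior to receiving the first dose of study drug in this study", averaged with any central values from the preceding 15 days. For other measures: "Baseline of other assessments is defined as the last available value obtained prior to the first dose of study drug in this study". Protocol 7.1.1.1 agrees: "The following assessments will be performed prior to study drug administration".

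Three further rules matter:
- SAP 5.3 makes these date-derived windows govern all outputs. It takes the last of several values at a visit, but the maximum for CPK, WBC and liver tests.
- SAP 13.2, headed for safety parameters, takes the last value after baseline when assessments are repeated or unscheduled.
- SAP 10.1 counts subjects whose Hb, averaged over selected periods, is at least 10 g/dL. It does not say whether Day 1 belongs to the first period.

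**The concern.** One record cannot be both the reference and the first result measured against it. The note probably aims to keep early samples (Days 2 to 14) in Week 4, which is sensible, but as worded it also admits the pre-dose sample. Two programmers working from this text could produce different first-visit tables.

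At stake are the first in-study Hb mean and responder count, the first change in liver tests, WBC and CPK, and the first special-lab values for any subject without a later sample in the window.

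**Working it through.** **Windows.** The inputs are the target-day formula and window rules in SAP 13.1.
- Week 4: target 7 × 4 + 1 = Day 29; next target 7 × 8 + 1 = Day 57; half-gap (57 − 29)/2 = 14. The rule gives Days 15–43; with the note, Days 1–43.
- Week 24 ECG: target 7 × 24 + 1 = Day 169; 169 − 84 = 85 and 169 + 83 = 252. The rule gives Days 85–252; with the note, Days 1–252.
- Week 24 special labs: 169 − 42 = 127 and 169 + 41 = 210. The rule gives Days 127–210; with the note, Days 1–210.

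In each case the note brings Day 1, already assigned to Baseline, into the window.

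**Default last-value rule.** If any later value lies in the window, that value is used and Day 1 has no effect.

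**Route (a): Hb averaged over the window.** With n values including Day 1, the mean differs from the Day 1 value by (n − 1)/n of the difference that the later values alone would show. The pull toward Day 1 is therefore 1/n.

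| Visit pattern | Days in window | Share of Day 1 |
|---|---|---|
| 4-weekly | 1, 29 | 1/2 = 50% |
| 2-weekly | 1, 15, 29, 43 | 1/4 = 25% |
| Weekly to Week 4, then Week 6 | 1, 8, 15, 22, 29, 43 | 1/6 = 17% |

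Day 43 is also the lower edge of Week 8. If it is assigned there, the 2-weekly share is 1/3. SAP section 3 describes 2-weekly visits for the first 104 weeks and 4-weekly visits after that; the protocol synopsis gives 4-weekly visits for subjects previously on roxadustat. Both patterns are therefore relevant.

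**Route (b): maximum rule (CPK, WBC, liver tests).** Let b be the Day 1 baseline and x one later value. With Day 1 in the window, the change is max(b, x) − b, which is never below 0. For independent normal values with equal SD and no true change, its mean is SD/√π = 0.56 SD, against 0 without Day 1. A simulation of 400,000 subjects agrees and gives the other cases, in SD units:

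| True change | Later values | Mean change without Day 1 | With Day 1 |
|---|---|---|---|
| 0 | 1 | 0.00 | +0.56 |
| +0.5 | 1 | +0.50 | +0.85 |
| −1.0 | 1 | −1.00 | +0.20 |
| 0 | 3 | +0.85 | +1.03 |

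With three later values the maximum rule itself accounts for most of the rise, and Day 1 adds 1.03 − 0.85 = 0.18 SD. Protocol Appendix A schedules chemistry every 4 weeks, so one later value (Day 29) is the natural case for liver tests. WBC, sampled with each CBC, may have three.

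Independence is an assumption. With within-subject correlation ρ the one-value figure becomes SD × √((1 − ρ)/π): 0.40 SD at an assumed ρ of 0.5 and 0.25 SD at 0.8.

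**Route (c): Day 1 is the only value in the window.** The documents give no rate for this. If m of the 15 subjects contribute a zero change in this way, the mean change shrinks by m/15: 7%, 13% or 20% for m = 1, 2 or 3 (assumed). A subject whose treatment ends before any later special-lab sample is one way it could arise, because SAP 13.1 stops analysis visits at end of treatment.

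**The case against.** A reader might infer that the note pulls all first changes (Hb, BP, ECG, hepcidin, hs-CRP) toward zero and narrows their SDs and confidence intervals. The documents do not support that.

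- Averaging is not the general rule. SAP 5.3 takes the last value, so the 25% and 50% figures do not apply to BP, ECG, chemistry, iron or special labs. Explicit averaging over periods appears only in the Hb count in SAP 10.1, which is not a change from baseline. Hb change appears among the safety laboratories in SAP 11.2.
- SAP 13.2 admits only values after baseline. On a plain reading this keeps the pre-dose record out of last-value safety summaries, ECG included. Its heading does not reach Hb as an efficacy endpoint or clearly reach special labs, and its last-value rule does not match the maximum rule in 5.3.
- A reused Day 1 value need not give a change of exactly zero. Baseline Hb can be a mean over 15 days, and SAP 11.3 averages BP and heart rate over the last 2 weeks of screening.
- Protocol 7.1.1.1 lets ECG and special-lab baselines come from the previous study's final visit, up to 4 weeks before dosing. Values dated before Day 1 cannot enter a window that starts on Day 1.
- Adding zeros does not always lower the SD. It raises it when the share of zeros p, the mean change m and the SD s satisfy (1 − p)m² > s².

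The note might also be read as describing the Baseline visit. That would repeat the Day 1 row, but it would do no harm: the specific Hb definition in SAP 5.3, which includes values from the 15 days before Day 1, would still apply. Finally, the column for actual assessment day carries a + marker with no footnote text in the available copy, and such a footnote could settle the matter.

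These points stand, and they reduce the concern to the three routes above.

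**Conclusion.** The double assignment of Day 1 is explicit, and since SAP 5.3 lets the windows govern every output it is a rule that can misplace a pre-dose value. Its reach is narrow: Hb period means, maximum-rule tests, and Hb efficacy or special-lab values with no later record in the window. There is no single direction of bias. Routes (a) and (c) pull toward the Day 1 value, while route (b) pushes upward.

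The sizes are conditional. The Hb shares require that the window is averaged. The 0.56 SD requires one later value, no true change, independence, and Day 1 serving as baseline. The m/15 figures use assumed counts.

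The defect is minor. The study is descriptive, without a power calculation, and only the first in-study summaries are affected. According to SAP section 3 all 15 subjects were already taking roxadustat, so Baseline is not an untreated value and the first window does not show a first response to the drug.

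**What to change.** Replace the note in SAP 13.1 with: *The first post-baseline visit window starts after the first dose of study drug in this study (Day 2, or a Day 1 value documented as post-dose); values taken before the first dose are used for baseline only, including for Hb period means and for parameters summarised by the maximum.*

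This keeps the benefit of the wide first window: Week 4 becomes Days 2–43, Week 24 ECG Days 2–252 and Week 24 special labs Days 2–210. The clause on documented post-dose Day 1 values prevents such a measurement from falling outside both Baseline and the first visit.

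The cost is one sentence and one programming condition. No post-dose data are lost, and if tables already exist only outputs that use the first window need rerunning.
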